Using the same methods as in Aim 1 (IRB-approved flyer and personalized invitations), random subset of $n=30$ intervention participants (10 from each of the three sites) and $n=36$ healthcare team members will be asked to complete key informant interviews. We will target the same 36 care team members who completed aim 1 interviews but, due to staff turnover, it is possible we may enroll those who did not participate in Aim 1.

An important process measure of Aim 3 is intervention dose, yet the total dose of complex multi-component interventions is often difficult to conceptualize. As part of a Diversity Supplement of the parent grant awarded to [name], we will re-engage the design team members that have participated in sub-aim 1.1 and aim 4 intervention adaptations to participate in a 2-part process of constructing a composite measure of total dose as described below and in Appendix T.

Aim 4 Enrollment:

Intervention Adaptation

Participants in the adaptation design team have already been identified as described in sub-aim 1.1, and have participated in the adaptation of the aim 2 trial. All original 20 design team members agreed to be contacted for future research, and will therefore be invited to participate in the aim 4 intervention adaptation process. Those members who agree to participate in aim 4 will be consented virtually and sent an invitation to participate in two zoom meetings, as described in the study procedures section.

Implementation-Effectiveness Trial

The aim 4 implementation study will enroll 110 participants ($n=35$ at each site) in the virtual arm. We have previously estimated the number of eligible participants at each site (Table 5). These numbers demonstrate the feasibility of our proposed new enrollment (~10x the enrollment goal).

Table 5: Estimated eligible participants at each clinic site.				
	High BP	High Cholesterol	Both*	High BP only *
MetroHealth	491	501	286	205
Duke	605	397	291	314
University Hospitals	550	485	334	216
* Those with both conditions are eligible for the parent trial, and those with high BP only are eligible for the virtual arm.				

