- **Part 2: Delphi Process:** This part of the study will further refine the list of variables generated during the group concept mapping phase to create a final composite measure of dose that incorporates different weights given to variables based on what stakeholders believe to be the most important aspects of the intervention. There will be 3 rounds of questionnaires to complete online and the total time required will be ~30-45 minutes.

The final composite measure of dose that results from this process will be used in analyses as a potential mediator of EXTRA-CVD outcomes, including both primary and secondary clinical outcomes (BP & cholesterol) but also implementation outcomes and other outcomes of interest (i.e. time to disengagement for those who are lost to follow-up).

Aim 2 Procedures:

We will conduct a randomized controlled trial of the EXTRA-CVD intervention vs. education control among PLHIV on suppressive ART who have both hypertension and hypercholesterolemia. Control participants will receive general prevention education. The intervention—contextually adapted during sub-aim 1.1—will consist of prevention education plus 4 additional evidence-based components: (1) **nurse-led care coordination**, (2) **EMR alerts and decision support**, (3) **home BP monitoring**, and (4) **nurse-managed medication protocols and adherence support**. The primary outcome is change in systolic BP and the secondary outcome will be change in non-HDL cholesterol. Separately for hypertension and hypercholesterolemia, we will then examine changes in the three extended treatment cascade categories [(1) % appropriately diagnosed, (2) % appropriately managed, and (3) % at treatment goal]. We chose BP as the primary outcome because the EXTRA-CVD intervention components

were designed primarily to address BP management, with cholesterol management being an important but secondary consideration. For the purposes of determining cascade level #1, we will use the following table to search for diagnosis of high cholesterol or blood pressure in the medical record.

Table: Diagnosis terms for high cholesterol and high blood pressure for the purposes of determining cascade category from chart review.

High Cholesterol	High Blood Pressure
Hyperlipidemia	Hypertension
Dyslipidemia	Essential Hypertension
Hypertriglyceridemia	Secondary Hypertension
Hypercholesterolemia	Hypertensive end-organ disease
Elevated LDL	High blood pressure
Elevated Triglycerides	
Elevated Cholesterol	

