1. Care coordination. Beginning with initial enrollment, the prevention nurse will coordinate blood pressure and cholesterol management for all participants in the intervention arm. Care coordination will consist of tailored discussions with the participant and his/her providers about which provider will take primary responsibility for BP and cholesterol management. Considerations of patient-provider trust and provider comfort level or experience will inform this decision. The prevention nurse will direct subsequent management decisions to the designated provider but will facilitate communication by notifying the non-designated of any changes to medications.

At the baseline visit, the prevention nurse will map the participant’s care team and communication preferences, to ensure that all providers in the patient’s care team are accounted for. After the initial visit, the nurse will contact members of the participant’s care team through normal clinical communication channels which are standard of care for that clinic site (e.g. EMR messages, email, phone) to inform them that the participant has been enrolled in the study. The prevention nurse may use this opportunity to discuss any potential modification to suggested blood pressure and cholesterol targets.

In order to better incorporate the prevention nurse into clinic workflow, a number of recommendations were made by the design teams. These include having nurse meet & greet and regular staff updates on the study to ensure that communication preferences are respected.

Component 1—Relevant process evaluation data for aim 3: (1) number and duration of telephone calls and emails to providers or providers’ staff; (2) number and nature of communication notes

in EMR; (3) prevention nurse trust & communication ties with providers; (4) time spent coordinating care.

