3. Home BP monitoring. Our justification for using home BP monitoring in the EXTRA-CVD intervention is that home BP measurements are reproducible with standard deviations of less than 3.1 mmHg for both systolic and diastolic measurements⁸⁴. In addition, home BP monitors are accurate and comparable to ambulatory BP monitors⁸⁵, a ‘gold standard’ of BP measurements. Home measurements have greater predictive power for mortality as compared to office-based measurements.⁸⁶ All intervention participants will receive a home BP monitor and will be trained according to a developed protocol¹⁴ and documentation of proper usage will be recorded. Participants will use the BP monitors every day. Prior to each telephone or in-person follow-up visit, we will request BP values for the past two weeks using a standardized data collection form. Participants with poor BP control will receive nurse calls every 2 weeks, with management changes made as described in component #2 above. All intervention participants will be able to keep the BP monitor after completion of the study. Control participants will receive a BP monitor and instructions about its use after completion of the final 12-month trial visit.

Component 3—Relevant process evaluation data for aim 3: (1) Frequency of home BP checks (average checks/week and proportion of weeks with ≥ 2 checks); (2) Number and nature of medication changes in response to home BP data; (3) Barriers to home BP use; (4) Knowledge of proper home BP use.

4. EMR support tools. Evidence-based EMR tools that do not result in provider fatigue or information overload effectively improve patient outcomes^{87,88}. Our three sites use two of the most widely available EMR systems (Epic at MetroHealth/Duke and Allscripts at UH). At the UH Special Immunology Unit, there is also a parallel electronic database that may be used for clinical purposes and is amenable to programmable tools. Beginning in year 1, we will work locally with EMR (IT) support to develop these tools to assist the prevention nurse during the intervention phase:

- An extended treatment cascade graphic for the prevention-nurse specialist which will appear on his/her “dashboard” or as a recurring pdf report. During the intervention phase, the nurse will have regular access to this graphic and will receive names of specific patients who have fallen out of each cascade category.
- Tool to chart home blood pressures in EMR.

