1. PROTOCOL SUMMARY

Study Description: This study uses mixed-methods approaches and stakeholder feedback to develop a composite measure of dose (i.e. the dose delivered and dose received) to explain the effectiveness of the EXTRA-CVD intervention of the parent study [*A nurse-led intervention to EXTend the HIV TReatment cAscade for CardioVascular Disease prevention (EXTRA-CVD); (U01HL142099)*].

Aim: To develop a pragmatic dose composite measure (i.e., the frequency and intensity) for the EXTRA-CVD intervention.

Objectives: Use a group concept mapping approach of stakeholder engagement and the Delphi method to formulate the dose composite measure.

Endpoints: Dose composite measure of the parent study, EXTRA-CVD.

Study population: Stakeholders, including those who have participated in previous stakeholder activities for the parent study (design team). These individuals include the EXTRA-CVD nurses, physicians, social workers, dieticians etc.

Study duration: 6 months

2. SCHEDULE OF ACTIVITIES (in months)

Activity	M-1	M-2	M-3	M-4	M-5	M-6
Finalize protocol & obtain IRB approval	X					
Send invitations to participants	X					
GCM steps 1 to 4		X	X			
GCM steps 5 & 6				X		
Delphi rounds 1 to 3					X	

Protocol

Share findings with stakeholders & research team						X
---	--	--	--	--	--	----------

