3. BACKGROUND

Within United States HIV clinics, there is limited evidence examining the effectiveness of implementation strategies to address the burden of comorbid HIV and atherosclerotic cardiovascular disease (ASCVD). Equally important to implementation effectiveness is the dose of an intervention – i.e. the frequency or duration of exposure to the intervention. Research from evidence based interventions (EBIs) underscore the importance of dose on the adoption and sustainability of interventions within routine practice care settings. While agreement on the link between dose and intervention outcomes is clear, there is less evidence in support of the development of optimal dose composite measures for EBIs, particularly pragmatic measures which include stakeholder feedback.

Stakeholder-engaged research is an important driving force for the implementation of science-led behavioral interventions, particularly as it pertains to engaging stakeholders early and frequently throughout the implementation period. More importantly, while most approaches for stakeholder-engaged research typically incorporate qualitative methods, robust mixed-method approaches such as group concept mapping (GCM) are increasingly being applied to implementation research for a number of reasons including developing criteria for pragmatic measures. GCM is a novel, participatory approach to stakeholder engagement and topic development, whereby the perceptions of participants on a specific subject are elicited and then used to generate illustrative conceptual frameworks of the target group or end-users views.

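### Relating end-of-study total dose to time to disengagement among those lost builds in a protective association, to the extent that dose is a cumulative count

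*Combined protocol and SAP*

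**What the plan says.** In the protocol's Sub-Aim 1.1 Procedures, the paragraph that follows the Delphi step states: "The final composite measure of dose that results from this process will be used in analyses as a potential mediator of EXTRA-CVD outcomes". The outcomes listed are blood pressure, cholesterol, implementation outcomes and "other outcomes of interest (i.e. time to disengagement for those who are lost to follow-up". Appendix T, section 3 (Background), repeats this.

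The documents describe dose in several ways:

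- Protocol section 7, Aim 3 Enrollment, says that "the total dose of complex multi-component interventions is often difficult to conceptualize" and that the design team will take part in "constructing a composite measure of total dose as described below and in Appendix T".
- Appendix T, section 3, defines dose as "the frequency or duration of exposure to the intervention".
- Appendix T, section 1, gives the aim as: "To develop a pragmatic dose composite measure (i.e., the frequency and intensity) for the EXTRA-CVD intervention".
- The candidate components are the process-evaluation data listed under Aim 2 Procedures. Most accumulate, for example "number and duration of telephone calls and emails to providers" under component 1, or algorithm use and telephone contacts under component 2. At least one is written as a rate: "average checks/week and proportion of weeks with ≥ 2 checks" under component 3.

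Appendix T, section 8 (Data Analysis), covers only how the composite is built. The Aim 2 SAP does not mention dose. Neither gives a time-to-event model, a censoring rule, a fixed early window for dose, or a dose updated over time.

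**The concern.** A participant who leaves at month 3 cannot receive most of the contacts planned for months 4 to 12. A cumulative dose measured at the end of the study is therefore partly a clock for the time that the participant stayed. Related to time to disengagement, it looks protective even if contact does nothing. This is immortal-time bias. It is separate from the confounding that arises because contact frequency is driven by clinical triggers.

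The wording about those lost to follow-up adds a second problem. Analysing only people who had the event selects on the outcome and leaves out the retained majority, who carry most of the information on staying engaged.

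At stake is an Aim 3 statement that more nurse contact keeps people engaged, reported from an analysis that could not have shown otherwise.

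**Working it through.** The documents give no figure for this analysis, so there is none to reproduce. The check is whether the planned comparison returns a null result when the truth is null.

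**Inputs from the protocol**
- 300 participants randomized 1:1, so 150 in the intervention arm (section 6, Aim 2).
- Loss of 5%, 10% and 15% at 4, 8 and 12 months, with 80-88% retention in prior studies, that is 12-20% lost (Statistical Considerations, Power). Expected number lost: 0.15 × 150 = 22.5.
- Minimum contacts: visits at 0, 4, 8 and 12 months, a 2-week call and mid-period calls (Aim 2 Procedures, Frequency of contact). I take the mid-period calls as months 2, 6 and 10. Further contacts are possible at up to 2-week intervals.

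**Assumptions, not in the documents:** the number and spread of further contacts, and that they are unrelated to leaving and stop when the participant leaves.

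**By hand, minimum schedule only** (contacts at 0, 0.5, 2, 4, 6, 8, 10 and 12 months)
- Leaves at month 3: 3 contacts. Leaves at month 9: 6 contacts. Retained: 8 contacts. Dose is a step function of time engaged.
- Divided by time engaged: leaves at month 1, 2/1 = 2.00 per month; month 3, 3/3 = 1.00; month 9, 6/9 = 0.67; retained, 8/12 = 0.67. The early contacts are front-loaded, so the ratio is highest in those who leave first.

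**Models.** Let T be the time to disengagement and D(t) the contacts received up to t.
- Fixed total dose: h(t) = h0(t)·exp(β·D(T)), with the retained censored at 12 months and D taken at month 12 for them.
- Time-updated: h(t) = h0(t)·exp(β·D(t)).
- Landmark: h(t) = h0(t)·exp(β·D(4)) for t > 4, in those with T > 4.
- Ratio: as fixed total dose, with D(T)/T.

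**Results with β = 0 and 15% lost** (median HR per contact; for the ratio, per contact per month; then percent with p < 0.05)

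| Contacts assumed | Spearman, lost | Total dose, lost only | Total dose, whole arm | Time-updated | Landmark | Ratio, whole arm |
|---|---|---|---|---|---|---|
| Mean 8 random a year, CV 0.5 | 0.61 | 66% | 0.74; 99% | not run | 4% | not run |
| Minimum + 6 a year, CV 0.7 | 0.81 | 0.716; 95.7% | 0.535; 100% | 0.997; 5.8% | 0.999; 5.1% | 2.87; 74.5% |
| Minimum + 18 a year, CV 0.5 | 0.79 | 0.859; 93.4% | 0.790; 100% | 0.995; 4.4% | 0.992; 3.6% | 1.33; 30.4% |

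The first row used 300 simulated trials and the others 1,000. At 1,000 trials the Monte Carlo standard error of a 5% rejection rate is √(0.05 × 0.95/1000) = 0.7 points, so the time-updated and landmark columns are close to nominal.

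Repeat runs of 400 trials gave, for the first row, 0.65, 68% (lost), 97% (whole arm) and 6% (landmark), and for the second row 0.82, 97%, 100% and 3%. A further separate set gave 78-98% (lost), 98-100% (whole arm), 5-7% (landmark) and 19-77% (ratio). At 15% lost the overall range is therefore about 66-98% among those lost and 97-100% in the whole arm.

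**Sensitivity.** Over 12-20% lost, for the two schedule-based rows: total dose 87.4-99.5% (lost) and 99.6-100% (whole arm); time-updated 4.4-5.8%; landmark 3.6-5.5%; ratio 28.0-83.6%.

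With the minimum schedule only, the correlation among those lost is 0.98 and significant in every trial. The Cox models then mostly cannot be fitted, the proposed ones included, because everyone engaged at a given month has the same count. The proposed models need real variation in triggered contacts.

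**Events left after a month-4 landmark.** 5% of 150 = 7.5 leave by month 4, so 22.5 − 7.5 = 15 remain. The loss is 7.5/22.5 = one third.

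**The case against.** The strongest reply is that the documents do not commit to a cumulative count entered as a fixed covariate. The composite was still to be built by concept mapping and Delphi. Total may mean summed across four components rather than over time, since Appendix T discusses how to weight one kind of call against another. The stated aim speaks of frequency and intensity, home BP use is expressed per week, and no model is named. All of this stands as a limit on certainty about the size. It does not remove the problem: adding up components that are themselves counts and minutes still gives a quantity that grows with time engaged. Nor does the text say whether the weekly home BP measure is taken over weeks engaged or over the whole 12 months.

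Second, the phrase about those lost may only say for whom a disengagement time is observed, without excluding the retained. That is possible. With the retained kept and censored but dose still taken at the end of the study, the false-positive rate is 97-100%, so the milder reading does not help.

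Third, some delivered effort may continue or rise as a participant drifts away. Provider calls and care-coordination time are candidate components, and the nurse makes at least three scheduling attempts before a letter is sent. This stands: the simulation leaves such effort out, and it could weaken the association.

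Fourth, none of the simulated models is a mediation analysis, which is the role the protocol names for dose. This also stands and shapes the fix.

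**Conclusion.** The concern holds, conditional on how the composite is built. To the extent that it is a cumulative count or duration of contacts, relating end-of-study dose to time to disengagement produces a protective association with no true effect. Under the assumed contact patterns and 15% loss, that happens in about 66-98% of trials among those lost and 97-100% in the whole arm. The direction was the same in every scenario. The size rests on assumed contact rates and on contacts stopping at disengagement.

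A reader might infer more than this, and the documents do not support it:
- That the analysis is bound to report a benefit whatever the truth. The measure was unbuilt and no model is stated.
- That the result would decide scale-up. The protocol discusses scale-up if the intervention proves effective but does not tie it to this analysis.
- That the trial's main conclusions are affected. This is an exploratory process analysis, and the primary systolic BP and secondary non-HDL tests do not use dose.

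It is still more than missing detail. The outcome, the group and the total-dose exposure are already written down, and followed in the natural way they give a biased answer.

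**What to change.** In the dose paragraph of Sub-Aim 1.1 Procedures and in Appendix T, section 3, state that:

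1. End-of-study total dose will not be used for time to disengagement.
2. All intervention participants are included, with those retained censored at 12 months.
3. The model is one of two, named in advance: a landmark model (dose received up to month 4 among those still engaged at month 4, later disengagement by Cox regression) or a Cox model with time-updated cumulative dose.
4. Total dose divided by time engaged will not be used. Because contacts are front-loaded, it gives a spurious harmful effect.
5. The result is a within-arm association, not an estimate of how far dose mediates the effect of randomized arm.

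The cost is one paragraph in two places. No new data are needed, provided that contacts are logged with dates. The landmark drops about one third of the events (roughly 15 of 23 remain), so precision will be low, and those who leave before month 4 should be described separately. The time-updated model keeps all events. Neither model removes confounding from trigger-driven contact, and the report should say so.
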